Enrollment of approximately 54 participants is planned for this clinical study. Optimally, each cohort of 9 participants will include 5 non-Japanese participants and 4 Japanese participants (this ratio is desired but not mandatory).

Note: *Enrolled* means participants, or their legally acceptable representatives, agreement to participate in a clinical study following completion of the informed consent process. Potential participants who are screened for the purpose of determining eligibility for the study, but do not participate in the study, are not considered enrolled, unless otherwise specified by the protocol. A participant will be considered enrolled if the informed

consent is not withdrawn prior to participating in any study activity after screening and if they are deemed eligible during the screening period.

Study Duration:

[figure not shown]
The total duration of the clinical study per participant will be up to 102 days (approximately 4 months), including the screening period.

Data Monitoring/Other Committee:

A safety monitoring committee (SMC) will be established for this study. When at least 7 participants have completed \geq 14 days in a cohort, a review of the safety data will be performed by the SMC to authorize opening of the next cohort. The details of the SMC structure and its roles and responsibilities will be documented in the SMC charter.

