4.1 Overall Design

This is a phase 1, randomized, placebo-controlled, double-blind, single ascending dose, FIH study to assess the safety, tolerability, PK, and PD of VIS954 administered SC in healthy participants.

The study will be conducted in 6 sequential cohorts. Each cohort will enroll 9 participants, randomized to VIS954 or placebo at a ratio of 7:2 (7 VIS954:2 placebo). Each cohort will also optimally enroll 5 non-Japanese participants and 4 Japanese participants (achievement of this ratio is desired but not mandatory to advance to the next cohort). No more than one Japanese participant per cohort may be randomized to receive placebo.

The study is comprised of:

- A screening visit up to 28 days before dosing
- An in-house stay for 4 days, with admission to the study center on Day −1, SC administration on Day 1, and discharge on Day 3
- A postdose period with outpatient visits on Days 5 (± 2 days), 8 (+ 1 day),
 11 (± 1 day), 15, 22, 29, 36, 43, and 57 (for all visits not otherwise specified, ± 3 days)
- A final follow-up visit on Day 71 (± 3 days)

The total duration of the clinical study per participant will be up to 102 days (approximately 4 months), including the screening period.

Potential participants will be carefully screened for eligibility prior to study enrollment.

On Day 1, a single dose of VIS954 or placebo will be administered SC.

Sentinel participants will be utilized in each cohort; the first 2 non-Japanese participants in each cohort will be randomized to receive either VIS954 (n = 1) or placebo (n = 1) and will receive the study intervention at least 24 hours before the remaining 7 participants in the cohort are dosed. The safety data from each of the 2 sentinel participants will be reviewed over the 24-hour postadministration period to determine whether it is appropriate to proceed with dosing of the remaining participants in the cohort as planned. A similar review will occur for each dose escalation. The remaining 7 participants in a cohort will be randomized to receive VIS954 (n = 6) or placebo (n = 1).

Escalation to next dosing level will occur after review of blinded safety data when at least 7 participants have completed \geq 14 days in a cohort.

The planned dose of VIS954 for each cohort is summarized in Table 4.1-1.

Table 4.1-1 Study Intervention for Each Cohort						
Cohort	Study Intervention					
Cohort 1	VIS954 or placebo					
Cohort 2	VIS954 or placebo					
Cohort 3	VIS954 or placebo					

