9.4 Sample Size Determination

The sample size for this FIH study was not based on formal statistical determinations. The sample size for this study was chosen in consideration of limiting exposure to this new chemical entity while providing sufficient information to evaluate the safety and tolerability of VIS954 in a phase 1 setting.

10 Supporting Documentation and Operational Considerations

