## 6.6. Retests, Unscheduled Visits and Early Termination Data

In general, for by-visit summaries, data recorded at the nominal visit will be presented. Unscheduled measurements will not be included in by-visit post-baseline summaries but will contribute to the best/ worst-case value where required (e.g., incidence tables for abnormal results by visit and treatment). In the case of a retest (same visit number assigned), the last available measurement for that visit will be used for by-visit summaries.

Early termination data will be mapped to the end of study visit number for by-visit summaries. Listings will include scheduled, unscheduled, retest and early discontinuation data.

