#### 15.1. Serum Concentration Data

Participants with partial data will be evaluated on a case-by-case basis to determine if sufficient data are available for reliable estimation of PK parameters.

Whole blood samples will be collected for measurement of serum concentrations of VIS954 at the time points specified in protocol Section 1.3. A listing of PK blood sample collection times as well as derived sampling time deviations will be provided. Samples that are outside the protocol-specified collection windows (calculated from the time zero point [e.g., time of drug administration] or the last relevant activity) will be identified, as well as participants that are excluded from the PKAS.

Serum concentrations will be summarized using descriptive statistics by Japanese versus non-Japanese, ADA status (positive and negative) and overall, for each treatment group. Results for samples which were collected outside the specified collection window will be included in the descriptive statistics and will be included in the calculation of PK parameters unless otherwise warranted by the data (i.e., in case of a protocol deviation impacting the validity of the sample collected such as a predose sample collected after dosing, or a postdose sample collected prior to dosing, etc.), but such results will be flagged in the listing. Concentrations that are below the limit of quantitation (BLQ) will be treated as zero for the computation of descriptive statistics.

A by-treatment participant listing of all concentration-time data for each cohort will be presented. Figures of arithmetic mean concentration-time data (±SD, as appropriate) will be presented for each cohort, by Japanese versus non-Japanese and ADA status (positive and negative) within each treatment group on linear and semi-logarithmic scales. Individual participant concentration-time data will be graphically presented on linear and semi-logarithmic scales using different symbols for Japanese and non-Japanese participants. All concentrations of VIS954 which were found to be BLQ for the PK assay during analysis will be imputed to and plotted at the nominal value of the LLOQ (25 ng/mL, i.e. 0.025 ug/mL) for all graphs which use a semi-logarithmic scale axis.

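### Early-termination values are summarised as Day 71 whatever day they were taken, which can distort Day 71 means in dose groups of seven

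*SAP*

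**What the plan says.** SAP 6.6 gives a general rule for tables by visit: "Early termination data will be mapped to the end of study visit number for by-visit summaries". It makes no condition on when the participant left.

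Three other places determine its effect:

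- **Protocol Table 1.3-1, footnote a**, moves the Day 71 assessments to the ET visit for anyone who discontinues. That column contains PK and RO sampling, hematology, chemistry and coagulation, urinalysis, vital signs and a full physical examination.
- **Protocol 4.1** defines the real visit: "A final follow-up visit on Day 71 (± 3 days", that is, Days 68 to 74.
- **SAP Appendix 1 (Presentation of Visits)** has a single combined row, V15, for end of study Day 71 and ET.

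For PK, SAP 15.1 adds: "Results for samples which were collected outside the specified collection window will be included in the descriptive statistics". It flags such samples in the listing and allows exceptions where the data warrant them. It also says: "Concentrations that are below the limit of quantitation (BLQ) will be treated as zero for the computation of descriptive statistics". The visible RO and safety sections (SAP 16.1, 18.2, 18.4 and 18.5) set no analysis window.

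**The concern.** After one dose, concentration and occupancy depend mainly on time since dosing. A sample from someone who leaves in the second or third week belongs to a different part of the curve from samples taken ten weeks after dosing. Under SAP 6.6 it is averaged with them and reported under the Day 71 visit.

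The late part of the profile is where a reader looks to see whether drug and occupancy have declined. For RO there is little else to look at: Table 1.3-1 schedules RO on Day 43 and then not again until Day 71, so no neighbouring late visit would expose an artefact. One early leaver could make a dose group look as if it still carries drug or occupied receptors. In the laboratory, vital-sign and physical-examination tables, a value from the first weeks would be reported as an end-of-study value.

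**Working it through.** **Group size.** Protocol 4.1: "The study will be conducted in 6 sequential cohorts" and "Each cohort will enroll 9 participants, randomized to VIS954 or placebo at a ratio of 7:2 (7 VIS954:2 placebo". So 6 × 9 = 54, which reproduces the Synopsis figure: "Enrollment of approximately 54 participants is planned for this clinical study". That is 6 × 7 = 42 active (7 per dose) and 6 × 2 = 12 pooled placebo. Protocol 9.4 says "The sample size for this FIH study was not based on formal statistical determinations", so there is no power calculation to rework.

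**Concentration.** Assume log-linear decline from exit day d to Day 71 with half-life h, and the same true Day 71 level in all 7 participants. Relative to that level, the ET sample is R = 2^((71 − d)/h). The reported mean is (6 + R)/7 times the true one. The documents give neither h nor d, so both are assumed.

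| Assumed half-life | Exit Day 15 | Exit Day 29 | Exit Day 57 |
|---|---|---|---|
| 7 days | ×37.4 | ×10.0 | ×1.43 |
| 14 days | ×3.14 | ×2.00 | ×1.14 |
| 21 days | ×1.76 | ×1.43 | ×1.08 |

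Example, h = 14, d = 15: R = 2^(56/14) = 16, and (6 + 16)/7 = 3.14. For h = 21: R = 2^(56/21) = 6.35, and 12.35/7 = 1.76.

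Variations on the case h = 14, d = 15:

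- If the leaver is replaced (protocol 7.2) and the ET value stays in: (7 + 16)/8 = 2.88.
- In a stratum of 4, since PK is also summarised by Japanese status: (3 + 16)/4 = 4.75.
- If the other six are BLQ and set to zero, the whole Day 71 mean comes from the ET sample.

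**Median and SD.** In a simulation with R = 16 and an assumed lognormal CV of 40%, the median of 7 rose about 8% while the SD rose about 15-fold.

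**Receptor occupancy.** With six completers at a common value x and one ET value E, the mean shifts by (E − x)/7. For x = 0% and E = 80%, the mean is 80/7 = 11.4%, the SD is 30.2 and the median is 0. The largest possible shift is 100/7 = 14.3 points.

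**Safety rows.** One participant is 1/7 = 14.3% of a Day 71 row.

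**Chance that it happens.** Protocol 7.2 gives no rate and expects withdrawal to be uncommon. The chance of at least one withdrawal among 7 is 1 − (1 − p)^7: 13% at an assumed p of 2%, 30% at 5%, 52% at 10%. Across all 42 active participants it is 57% at 2% and 88% at 5%. These are upper figures for the problem, because the early visit is held only where possible.

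**Outputs checked and unaffected.** SAP 15.2 computes PK parameters from actual times since the dose. The time above 40% RO uses actual collection times. Scheduled ECGs end on Day 2, and injection-site and pain assessments on Day 29. TEAE incidence is not a table by visit.

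**The case against.** The strongest reply is that this is a contingent blemish in descriptive tables. It needs an early withdrawal and a completed ET visit. The row label tells the reader that the two kinds of visit are mixed. Medians are in the quantitative summaries, individual concentration and RO plots and a median RO plot are planned, and study day appears in dated listings. An SD of 30 around a mean RO of 11% would itself signal an outlier. SAP 15.1 permits exclusion of PK values where the data warrant it, and SAP 11.2 lists significant time deviations at key PK times. The table templates mentioned in SAP section 8 are not available here and might separate the visits.

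Much of this stands, and it limits the size of the problem. It does not remove it. The exclusion clauses are discretionary and do not name ET samples, and an ET visit that the protocol itself directs need not count as a deviation. A combined label does not say which values, or how many, come from another time.

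A reader might infer more: that Day 71 is the planned washout check, that safety reporting as a whole is compromised, or that dose escalation could be misled. The documents do not support this. Protocol 10.4.2 places the end of systemic exposure at Day 56, and no endpoint or decision rule uses a Day 71 mean. Escalation rests on committee review once at least 7 participants have completed 14 days, and SAP 4.1 puts that reporting outside its scope. SAP 6.7 plans no hypothesis tests.

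**Conclusion.** The point holds in limited form. Applied as written, SAP 6.6 puts values from the wrong time into the Day 71 summaries. The distortion falls on the mean, SD and maximum of concentration and %RO, on the last point of the mean curves (taking these to use the same visit assignment), and on the Day 71 laboratory, vital-sign and physical-examination rows.

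With one ET among 7 and half-lives of 14 to 21 days, the Day 71 mean concentration is about 1.8 to 3.1 times too high for a Day 15 exit and about 1.1 times for a Day 57 exit. A shorter half-life makes it larger. These multipliers rest on an assumed half-life, exit day and log-linear decline, so they are illustrations and not predictions. The existence of the rule is certain; its effect depends on who withdraws and when. It is worth correcting before final tables are produced because the correction is nearly free.

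**What to change.** In SAP 6.6, replace the mapping sentence with:

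> Early termination data will be summarized in a separate Early Termination row, with actual study day listed, and will not contribute to Day 71 by-visit summaries or mean/median plots unless collected within the Day 71 window (Days 68-74). Day 71 visits of participants who complete the study stay under the nominal visit.

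In Appendix 1, split the combined V15 row into a Day 71 row and an ET row.

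Two alternatives are less good. Restricting Day 71 to Days 68 to 74 for everyone would also drop completers seen late, against the nominal-visit rule in SAP 6.6 and the retention of out-of-window samples in SAP 15.1. Re-mapping each ET visit to the nearest scheduled visit needs a tie-break when that visit was already attended. It would also create rows with n = 1 on days without scheduled laboratory tests, such as Day 8.

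The cost is SAP wording, a small change to visit mapping and one extra row. The Day 71 n falls by the number of participants whose ET visit lies outside the window. In the example of one ET among 7, n becomes 6 and the inflation factor returns to 1.

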#### 6.7. Statistical Tests

No formal statistical testing of hypotheses will be conducted. Exploratory statistical analyses may be carried out without drawing any inference, as documented in Section 3.3.

#### 6.8. Common Calculations

For quantitative measurements, change from baseline will be calculated as:

Test Value at any post baseline Visit X – Value at Baseline assessment.

#### 6.9. Software Version

All derivations, statistical analyses, summary tables, listings, and graphical figures will be generated using SAS version 9.4 or higher (SAS Institute, Inc., Cary, North Carolina). Non-compartmental PK parameter calculations will be performed using Phoenix® WinNonlin® 8.3 or higher (Certara, L.P. Princeton, New Jersey, United States of America [USA]).

Page 21 of 42

### 7. STATISTICAL CONSIDERATIONS

# 7.1. Missing Data

Missing safety data will not be imputed.

Missing PK data will be handled as described in Section 15 of this analysis plan.

### 8. OUTPUT PRESENTATIONS

APPENDIX 1 shows conventions for presentation of data in outputs.

The templates provided with this SAP describe the presentations for this study and therefore the format and content of the summary tables, figures, and listings to be provided by IQVIA Biostatistics.

Some minor modifications may be necessary to the planned design of tables, figures, and listings to accommodate emerging data collected during the actual study conduct.

## 9. DISPOSITION AND WITHDRAWALS

All participants who provide informed consent will be accounted for in this study. Participant disposition will be tabulated for each treatment group and for all participants combined with the number of participants who are screened, randomly assigned to treatment, dosed, complete the study, prematurely discontinue, with the reason for early discontinuation. The number of participants in each of the analysis sets will also be included in the disposition table. A listing will present dates of completion or early withdrawal and the reason for early discontinuation, if applicable, for each participant.

Listings of inclusion/exclusion criteria failures, study eligibility, subject reconsent and rescreening, treatment assigned based on randomization with date and time of study treatment administration will be provided.

Statistical Analysis Plan Page 22 of 42

### 10. DEMOGRAPHIC AND OTHER BASELINE CHARACTERISTICS

Individual participant demographics and baseline characteristics (medical history and results from drug and alcohol screens, serology screening, and pregnancy tests) will be presented in listings.

Demographic characteristics such as age, sex, race, ethnicity, height, weight, and body mass index (BMI) will be summarized and tabulated by treatment, for all active-treated participants, for Japanese and non Japanese participants, and for all participants overall for the safety analysis set. Descriptive statistics will be presented for age, height, weight, and BMI. Frequency counts and percentages will be presented for sex, race, ethnicity, and if the participant belongs to the Japanese or to the non-Japanese group. No statistical testing will be carried out for demographic or other baseline characteristics.

#### 10.1. Derivations

BMI (kg/ m²) = weight (kg)/ height (m)²

### 11. PROTOCOL DEVIATIONS

# 11.1. Deviations Related to Study Conduct

A deviation from a protocol occurs when Investigator site staff or a study participant does not adhere to the protocol's stipulated requirements, whether inadvertently or planned. Protocol deviations will be listed and will include a classification of minor or major, as determined by clinical and medical staff.

Protocol deviations will be reviewed by the study pharmacokineticist and biostatistician prior to unblinding to identify deviations which have the potential to affect the PK, PD, CCI

# 11.2. Deviations Related to PK, PDCCI

Changes to the procedures or events, which may impact the quality of the PK, PD, CCI data, will be considered important protocol deviations, and will be described within the clinical study report body text. These changes or events will include any circumstances that will alter the evaluation of the PK, PD CCI

Examples include, but may not be limited to:

- Deviation from inclusion and/or exclusion criteria with potential to affect PK, PDCCI
- Deviation from study restrictions with potential to affect PK, PDCCI
- Concomitant medications that can affect PK, PDCCI
- Missed, incomplete, or incorrect dosing.
- Sample handling/processing errors.
- Bioanalytical issues affecting the data.
- Missing concentrations/not collected samples at key times in PK profile.
- Significant time deviations at key times in PK profile.
- Other protocol deviations with potential to affect PK, PDCCI

In the case of an important protocol deviation or event, PK, PD data collected during the affected treatment period will be excluded from the study results. Excluded data and the reason(s) for exclusion will be described in a listing. A summary of important protocol deviations will be tabulated by treatment group. Other changes to the procedures or events which do not impact the quality of the PK and PD data will not be considered important protocol deviations. A common example of a non-significant protocol deviation is a missed blood sample or deviations from blood collection times (that do not occur at key times in the profile).

[figure not shown]

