# 5.6. Pharmacodynamic Analysis Set [PDAS]

The pharmacodynamic analysis set (PDAS) will contain all participants who receive study medication (active or placebo) and have at least 1 measured PD value at a scheduled time point after start of dosing. Participants in this population will be used for all PD analyses.

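### SAP 11.2 excludes PK and PD data by treatment period, so in this single-dose trial a fault in one sample can remove a participant's whole post-dose record from the summaries

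*SAP*

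**What the plan says.** SAP 11.2 treats as important any change or event that may impair the quality of the PK or PD data. Its examples mix events that touch the whole participant, such as dosing errors and eligibility breaches, with faults in individual samples: "Sample handling/processing errors", bioanalytical problems, "Missing concentrations/not collected samples at key times in PK profile" and "Significant time deviations at key times in PK profile". The consequence is the same for all of them: "PK, PD data collected during the affected treatment period will be excluded from the study results". There is one exemption. "A common example of a non-significant protocol deviation is a missed blood sample or deviations from blood collection times", provided that the sample is not at a key time. Key times are not defined.

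Other sections bear on the same events:

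- **SAP 5.5** limits the PK analysis set, used for all PK analyses, to participants free of deviations or events that could affect PK evaluation.
- **SAP 5.6** admits to the PD analysis set those who received study medication and "have at least 1 measured PD value at a scheduled time point after start of dosing". It has no deviation clause.
- **SAP 15.1** sends partial profiles to case-by-case judgment. On timing it says: "Results for samples which were collected outside the specified collection window will be included in the descriptive statistics". Such samples also enter the parameter calculations and are flagged, unless a deviation undermines the sample's validity.
- **SAP 15.2** calculates PK parameters from actual elapsed time.
- **Protocol 4.1** sets the design: "On Day 1, a single dose of VIS954 or placebo will be administered SC". The last visit is Day 71.

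**The concern.** An exclusion rule defined by treatment period does limited damage in a trial with several periods, because the unaffected periods survive. Here each participant has one dose and one follow-up, so nothing survives. A rule that reads as a partial exclusion becomes a participant-level exclusion, and some of its triggers are confined to a single tube of blood.

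The secondary PK and PD objectives rest on descriptive summaries of small groups. Sound values would leave those summaries for reasons unrelated to their own quality, and RO results could go because of a fault in a PK sample. Because 15.1 treats some of the same events differently, the reported summaries would also depend on which section the analyst follows.

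**Working it through.** 1. **Design count.** 6 cohorts × 9 = 54, which matches the planned enrolment. Of these, 6 × 7 = 42 are active and 6 × 2 = 12 placebo.

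2. **Treatment periods.** There is one dose per participant (Protocol 4.1), and neither document defines sub-periods. The affected period is therefore the participant's whole post-dose record.

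3. **Size of that record** (Protocol Table 1.3-1 and its notes).
   - PK: 4 samples at 4, 8, 24 and 48 hours, plus 10 on Days 5, 8, 11, 15, 22, 29, 36, 43, 57 and 71, giving 4 + 10 = 14.
   - RO: Days 2, 3, 5, 8, 11, 15, 22, 29, 36, 43 and 71, giving 11.

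4. **Loss from one PK sample fault.**
   - Sample-level rule: 1/14 = 7% of that participant's PK values, and 13 stay.
   - SAP 11.2 as written: all 14 if the sample was taken but faulty, or the remaining 13 if it was never collected. On the plain wording, the 11 RO values go as well.

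5. **Loss per group.**
   - Dose level: 1/7 = 14%.
   - Subgroup, at the desired mix of 4 Japanese and 5 non-Japanese: at most one Japanese participant is on placebo, so 3 or 4 Japanese are active. The non-Japanese active count is 7 − 3 = 4 or 7 − 4 = 3. One exclusion costs 1/4 = 25% or 1/3 = 33%.

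6. **SAP 11.2 against SAP 15.1, by event.**
   - Missed or late sample, not at a key time: a late sample is exempt under 11.2 and kept under 15.1, and a missed one is exempt under 11.2. No conflict.
   - Significantly mistimed at a key time, sample invalid: 15.1 lets that result be left out; 11.2 removes the whole record. They differ in extent.
   - Significantly mistimed at a key time, sample still valid: 15.1 keeps the value; 11.2 removes the record. Direct conflict.
   - Sample missing at a key time: 15.1 judges case by case; 11.2 excludes. Direct conflict.
   - Handling or bioanalytical error: 11.2 applies at any time point, with no key-time limit.

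7. **SAP 15.2 for comparison.** It usually works at sample or parameter level. Values below quantification embedded after Cmax are set to missing. Extrapolation above 20% removes only AUC0-inf, CL/F and Vd/F from the summaries.

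8. **Frequency.** The documents give neither a per-sample fault rate p nor the number m of samples that can trigger the rule. Purely as an assumption, with independent faults, P(participant excluded) = 1 − (1 − p)^m:
   - m = 3: p = 0.5% gives 1.5%; p = 2% gives 5.9%.
   - m = 14: p = 0.5% gives 6.8%; p = 2% gives 24.6%.

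   The spread shows that the frequency is undetermined. It is not an estimate, and steps 2 to 6 do not use it.

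**The case against.** The strongest reply is that the rule is not mechanical. An event must be capable of impairing data quality before it counts. The pharmacokineticist and biostatistician review deviations before unblinding (SAP 11.1). Protocol 9.2.7.1 lists excluded participants separately from excluded data, so exclusion at data level is foreseen. The term treatment period is undefined, and the schedule distinguishes treatment from post-treatment follow-up. PK and PD may be meant respectively, each excluded only for its own faults. The stakes are also bounded: these are secondary descriptive endpoints, there is no hypothesis testing (SAP 6.7), and the primary safety outputs use the safety set, which 11.2 does not touch.

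Part of this stands. Review before unblinding limits bias, and SAP 15 keeps PK data for all treated participants in the listings, so values leave the summaries and not the report. But the review decides whether an event is important; once it is, 11.2 prescribes the consequence without discretion. No narrower period is defined. Reading PK and PD respectively would still drop a full PK profile for one PK sample.

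Three stronger readings are tempting, and the documents do not support them:

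- A reader might infer that any late sample is kept by 15.1 and triggers exclusion under 11.2. The exemption in 11.2 rules that out for samples away from key times.
- A reader might infer that 5.6 contradicts 11.2. It does not: 5.6 decides who enters the PD set, and 11.2 decides which data are dropped.
- A reader might infer that the rule was carried over from a crossover template. The SAP says nothing about its origin.

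**Conclusion.** The point holds. Read as written, SAP 11.2 lets one handling or bioanalytical error, or one missing or significantly mistimed sample at an undefined key time, remove a participant's whole post-dose PK record, and on the plain wording the RO record, from the summaries. SAP 5.5 supports that outcome for PK. SAP 15.1 points the other way for partial data and, among mistimed samples, for significant deviations at key times that leave the sample valid.

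The cost per exclusion follows from the design: 14% of a dose group, and 25–33% of an ethnic subgroup if the desired enrolment mix is met. The frequency is unknown, so no expected loss is claimed. The conclusion assumes that the treatment period means the full post-dose follow-up, the only reading available while neither document defines a shorter one. The harm is mainly lost information and an unsettled rule; bias is a lesser worry, since the review precedes unblinding.

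**What to change.** Replace the exclusion sentence in SAP 11.2 with wording to this effect: *Only the affected samples, and the parameters that depend on them, are excluded. A participant's whole PK or PD profile is excluded only when an event invalidates the whole profile, for example missed, incomplete or incorrect dosing. A fault confined to PK samples does not exclude PD data, and a fault confined to PD samples does not exclude PK data.*

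Three further edits are needed for this to work:

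- Amend the deviation clause in SAP 5.5 to match. Otherwise the PK analysis set can still remove the participant from every PK summary.
- Define key times by listing the scheduled samples that count.
- Cross-refer to 15.1 for keeping out-of-window samples, and to 15.2 for the use of actual elapsed time in PK parameters.

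The change is to SAP wording only; sampling and trial conduct are unaffected. The cost is a few more case-level decisions to document before unblinding.
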